Appendix 6: Schedule of Assessments

Study Plan – Part A (Single Dose)

	Pre-screening ^d	Screening	Day -2	Day -1	Days 1 to 3	Day 4	Day 7 (± 2 days)	Day 10 (± 2 days)	Day 14 (± 2 days)	Poststudy (Day 28 ± 2 days)
Inclusion/exclusion criteria		X								
Demographic data		X								
Medical history		X								
Urine drugs of abuse screen		X	X							
Alcohol breath test		X	X							
Cotinine test		X	X							
Serology		X								
Hormone panel		X								
Urine pregnancy test ^a		X	X							X
Informed consent	X	X								
Study residency:										
Check-in			X							
Check-out					Day 3 (48 hours postdose)					
Non-residential visit	X	X				X	X	X	X	X
Study drug administration:					Day 1 (0 hours)					
Safety and tolerability:										
Adverse event recording		X	X	X	Ongoing	X	X	X	X	X
Concomitant medication recording		X	X	X	Ongoing	X	X	X	X	X
Supine blood pressure, pulse rate, respiratory rate, and body temperature		X			Predose, 1, 2, 4, 8, 24 (± 1 hour), and 48 hours postdose	X	X	X	X	X

	Pre-screening ^d	Screening	Day -2	Day -1	Days 1 to 3	Day 4	Day 7 (± 2 days)	Day 10 (± 2 days)	Day 14 (± 2 days)	Poststudy (Day 28 ± 2 days)
Supine 12-lead ECG		X			Predose, 4, 24 (± 1 hour) and 48 hours postdose		X		X	X
Continuous ECG extraction ^{b,c}				-24, -23.5, -23, -22.5, -22, -21.5, -21, -20, -18, -16, -12 hours	Day 1: Predose, 0.5, 1, 1.5, 2, 2.5, 3, 4, 6, 8, 12 and 24 hours					
Heat pain threshold test (heat pain threshold and heat pain tolerance)					Day 1: predose, 2, 4, 12, and 24 hours postdose (± 1 hour)					
Clinical chemistry, haematology, and urinalysis		X	X		48 hours postdose		X		X	X
Height and BMI		X								
Body weight		X	X							X
Physical examination		X								
Symptom-directed physical examination					Prior to discharge		X		X	X

	Pre-screening ^d	Screening	Day -2	Day -1	Days 1 to 3	Day 4	Day 7 (± 2 days)	Day 10 (± 2 days)	Day 14 (± 2 days)	Poststudy (Day 28 ± 2 days)
Injection site assessment					Predose, 1, 2, 4, 8, 24, 48 hours postdose		X		X	X
Pharmacokinetics^e										
Blood sampling					Predose, 0.5, 1, 1.5, 2, 3, 4, 6, 8, 12, 16, 24, 36 and 48 hours postdose	X	X	X	X	X
Pharmacodynamics^d:										
Intradermal capsaicin test (capsaicin-evoked pain and secondary hyperalgesia measurement)	X		X		Day 2 (The area of secondary area of hyperalgesia will be evaluated at 5 and 30 minutes post-capsaicin injection)					

Abbreviations: BMI = body mass index; ECG = electrocardiogram.

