^a A positive urine pregnancy test result will be confirmed with a serum pregnancy test.

^b All times are relative to dosing with OLP-1002.

^c Continuous ECG recording may begin at approximately 25 hours before dosing to allow for checks to be completed prior to the first extraction timepoint and will continue for 24 hours postdose, ie, until after the last timepoint for ECG extraction (24 hours postdose). At timepoints for ECG extractions, subjects will be supinely resting for a total of 15 minutes (10-minute supine rest period, 5-minute extraction). Data will be archived for potential future analysis and will not be available for review during the study.

^d Pharmacodynamic assessment groups only.

^e PK analysis in Part A will initially only be conducted for groups receiving $\geq 12 \mu\text{g}$ OLP-1002, with retrospective analyses of samples from lower dose groups occurring in the event of PK data being quantifiable at doses $\geq 12 \mu\text{g}$ and if supported by bioanalytical stability data.

Study Plan – Part B (Multiple Dose)

	Screening	Day -1	Days 1-15	Day 18 (± 2 days)	Day 22 (± 2 days)	Day 25 (± 2 days)	Day 29 (± 2 days)	Poststudy (Day 57 ± 2 days)
Inclusion/exclusion criteria	X							
Demographic data	X							
Medical history	X							
Urine drugs of abuse screen	X	X						
Alcohol breath test	X	X						
Cotinine test	X	X						
Serology	X							
Hormone panel	X							
Urine pregnancy test ^a	X	X			X		X	X
Informed consent	X							
Study residency:								
Check-in		X						
Check-out			Day 15 (48 hours postdose)					
Non-residential visit	X			X	X	X	X	X
Study drug administration:			Days 1, 4, 7, 10, and 13					
Safety and tolerability:								
Adverse event recording	X	X	Ongoing	X	X	X	X	X
Concomitant medication recording	X	X	Ongoing	X	X	X	X	X
Supine blood pressure, pulse rate, respiratory rate, and body temperature	X		Day 1: predose, 1, 2, 4 and 8 hours postdose Day 2, Day 4 (postdose), Day 5, Day 7 (postdose), Day 9, Day 10 (postdose), Day 12, Day 13: predose, 1, 2, 4 and 8 hours postdose, and Day 15	X	X	X	X	X

	Screening	Day -1	Days 1-15	Day 18	Day 22	Day 25	Day 29	Poststudy (Day 57 ± 2 days)
Heat pain threshold test (heat pain threshold and heat pain tolerance)	X		Day 1 and Day 13: predose, 1, 2, 4, 8, 24 hours postdose					
Supine 12-lead ECG	X		Day 1: predose and 4 hours postdose Day 4: predose and 4 hours postdose Day 7: predose and 4 hours postdose Day 10: predose and 4 hours postdose Day 13: predose and 4 hours postdose Day 15		X		X	X

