Clinical chemistry, haematology, and urinalysis	X	X	Days 2, 5, 9, 12, 17		X		X	X
Height and BMI	X							
Body weight	X	X						X
Physical examination	X							
Symptom-directed physical examination			Days 1, 4, 7, 10, 13		X		X	X
Injection site assessment			Day 1: predose and 4 hours postdose Day 4: predose and 4 hours postdose Day 7: predose and 4 hours postdose Day 10: predose and 4 hours postdose Day 13: predose and 4 hours postdose Day 15		X		X	X
Pharmacokinetics:								
Blood sampling ^b			Day 1 and Day 13: Pre dose, 0.5, 1, 1.5, 2, 3, 4, 6, 8 and 12 hours post dose Days 4, 7, 10 Predose Day 15	X	X	X	X	X

Abbreviations: BMI = body mass index; ECG = electrocardiogram.

^a Positive urine pregnancy test results will be confirmed with a serum pregnancy test.

^b PK timepoints will be reviewed based on emerging data and may be updated.

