1.4. Summary of Toxicology

In rats, following twice-weekly SC dosing for 13 weeks, OLP-1002-related microscopic findings included pigment accumulation in the kidney of males administered 100 nmol/kg/dose and females administered ≥ 10 nmol/kg/dose, foreign material and vacuolated macrophage infiltrates in males and/or females administered ≥ 1 nmol/kg/dose, and an increased incidence and/or severity of mononuclear cell infiltrates at the injection sites in males and/or females administered ≥ 10 nmol/kg/dose. These findings persisted through the recovery phase in animals administered 100 nmol/kg/dose. However, the effects were considered non-adverse due to their mild severity and lack of impact on animal health and wellbeing. The no-observed-adverse-effect level (NOAEL) was 100 nmol/kg/dose. This dose level corresponded to maximum observed plasma concentration (C_{max}) and area under the plasma concentration-time curve (AUC) from 0 to 24 hours postdose (AUC₀₋₂₄) values of 27.6 ng/mL and 174 ng·hr/mL, respectively, in males and 24.9 ng/mL and 128 ng·hr/mL, respectively, in females on Day 88 of the dosing phase.

In cynomolgus monkeys, following twice-weekly SC dosing for 13 weeks, OLP-1002-related microscopic findings included mononuclear cell infiltrates at the SC injection sites of animals administered ≥ 10 nmol/kg/dose. This finding was not resolved with the completion of the recovery phase. However, the effects of 100 nmol/kg/dose were considered non-adverse due to the mild severity of findings and the lack of impact on animal health and wellbeing. The NOAEL was 100 nmol/kg/dose (equivalent to 462.29 µg/kg/dose), which corresponded to C_{max} and AUC from 0 to 72 hours postdose (AUC₀₋₇₂) values of 121 ng/mL and 2840 ng·hr/mL in males, respectively, and 216 ng/mL and 4840 ng·hr/mL in females, respectively, on Day 88 of the dosing phase.

The genotoxic and mutagenic potential of OLP-1002 was evaluated with standard Good Laboratory Practice (GLP) via in vitro bacterial mutagenicity and chromosomal aberration studies, and was found to be negative.

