2.2. Endpoints

2.2.1. Primary Endpoints

The primary safety endpoints for this study are as follows:

- incidence and severity of AEs
- vital signs measurements (blood pressure, pulse rate, respiratory rate)
- 12-lead electrocardiogram (ECG) parameters
- incidence of clinical laboratory abnormalities, based on clinical chemistry, hematology, and urinalysis test results
- physical examinations
- injection site assessment.

- demonstrate that exposure to OLP-1002 does not exceed pre-defined exposure limits from non-clinical studies.

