3.1.2. Part B

Part B will comprise a multiple-dose, sequential-group study. Overall, 24 subjects will be studied in 3 groups (Groups B1 to B3), with each group consisting of 8 subjects. Up to 3 additional groups (24 subjects in total) may be included for further assessment of safety and tolerability ([Section 3.3](#)).

Potential subjects will be screened to assess their eligibility to enter the study within 28 days prior to the first dose administration. Each subject will participate in 1 treatment period only and reside at the CRU from Day -1 until Day 15.

All subjects will return for non-residential visits on Days 18 (± 2 days), 22 (± 2 days), 25 (± 2 days), and 29 (± 2 days), and for a poststudy visit on Day 57 (± 2 days).

[figure not shown]
In each of Groups B1 to B3, 6 subjects will receive OLP-1002 and 2 subjects will receive placebo. For all subjects, a single subcutaneous dose will be administered on Days 1, 4, 7, 10, and 13. Prior to each dosing occasion a physician will review the available safety and tolerability data from each subject to confirm it is acceptable to continue dosing. The dosing frequency in Part B may be changed following review of data from groups in Part A ([Section 3.4](#)).

Sentinel dosing will only occur in Part B at dose levels where exposure to OLP-1002 at steady state is predicted to exceed exposures that have been shown to be safe and well tolerated in earlier groups in Parts A or B. In the event of sentinel dosing, 2 subjects (1 active, 1 placebo) will be dosed at least 4 days prior to the remaining 6 subjects (5 active: 1 placebo). Safety data for the sentinel subjects from at least 2 additional doses will be reviewed prior to dosing the remaining subjects (i.e. sentinel subjects' safety data after doses 1 and 2 will be reviewed prior to the remaining subjects receiving dose 1). In addition, safety data from each subject will be reviewed by a physician prior to each dose to approve continued dosing.

Doses will be administered in an escalating manner following satisfactory review of safety, tolerability, and PK data up to Day 22 (216 hours post-final dose) from the lower dose levels. Part B may start after a review of the safety, tolerability, and available PK for Groups A1 to A6. The total daily dose administered will not exceed the highest single dose given in Part A.

An overview of the study design is shown in [Figure 2](#).

Figure 2: Study Schematic (Part B)

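### Part B schedules no graded injection site assessment between 4 h and 72 h after doses 1 to 4, so Grade 1–2 local reactions in that window are captured only if noticed or volunteered as AEs

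*Protocol*

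**What the plan says.** Section 2.2.1 lists "injection site assessment" among the primary safety endpoints. Section 7.3.8 defines it: pain, redness, swelling and tenderness are graded 0 to 4, and bruising and ulceration are scored as present or absent.

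The two study plans in Appendix 6 time it differently.

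- **Part A (single dose):** "Predose, 1, 2, 4, 8, 24, 48 hours postdose", then the Day 7, 14 and 28 visits.
- **Part B (repeated dose):** dosing is on "Days 1, 4, 7, 10, and 13". The site is assessed at "Day 1: predose and 4 hours postdose Day 4: predose and 4 hours postdose", likewise on Days 7, 10 and 13, then on Days 15, 22, 29 and 57.

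Part B subjects "reside at the CRU from Day -1 until Day 15" (Section 3.1.2). Staff already see them between doses: apart from the full profiles on Days 1 and 13, the in-house vital signs row includes "Day 2, Day 4 (postdose), Day 5, Day 7 (postdose), Day 9, Day 10 (postdose), Day 12", and laboratory samples are also taken on Days 2, 5, 9 and 12. No injection site assessment is attached to those four days.

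**The concern.** Part B is the part that tests repeated injection, yet after each of the first four doses its graded local-tolerability record has one early rating and then nothing until shortly before the next injection. Redness, swelling or tenderness that peaks at, say, 24 h and has settled by 72 h receives no scheduled grade.

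This matters because the AE route is not a full substitute for the graded endpoint. Under Section 7.3.8 a local rating has to become an AE only at Grade 3 or above, or if there is ulceration. Redness of 25 to 100 mm is Grade 1 or 2 and carries no such requirement. The daily questioning in Section 7.3.1 is open-ended; it does not measure a diameter or test for tenderness. If lower-grade reactions occur in the gap, the tabulated incidence by grade in Part B would tend to be too low, and these tolerability data also feed the review before each dose and each escalation decision (Section 3.1.2).

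**Working it through.** **Inputs** (all from Appendix 6): Part B dosing on Days 1, 4, 7, 10 and 13; site checks before dosing and 4 h after it on those days, then on Days 15, 22, 29 and 57; Part A postdose checks at 1, 2, 4, 8, 24 and 48 h, then on Days 7, 14 and 28.

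**Formula:** hours after a dose = 24 × (assessment day − dose day), with 4 h for the postdose check.

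**Check of the convention against the plan's own figures:** Day 15 after dose 5 is 24 × (15 − 13) = 48 h, which agrees with "Day 15 (48 hours postdose" in the check-out row. Day 22 is 24 × (22 − 13) = 216 h, which agrees with the figure in Section 3.1.2.

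**Scheduled graded checks after each dose, taking the predose check to cover the previous site:**

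| | Postdose checks (h) | Longest gap up to the last in-house check |
|---|---|---|
| Part B, doses 1–4 (each) | 4, 72 | 72 − 4 = 68 h |
| Part B, dose 5 | 4, 48, 216, 384, 1056 | 48 − 4 = 44 h |
| Part A, single dose | 1, 2, 4, 8, 24, 48, 144, 312, 648 | 48 − 24 = 24 h |

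The gap is 68/72 = 94% of each of the first four dosing intervals. Within 48 h of a dose there are six checks in Part A, one after each of Part B doses 1–4, and two after dose 5.

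**Times shared by the two parts:** 4 h after every dose, and 48 h after dose 5 only. The 72 h check has no Part A counterpart, because the Part A row is blank on Day 4.

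**Which site the 72 h check covers:** Section 7.3.8 speaks only of the dosing site. On Day 1 the predose check can only concern the site about to be used. If that meaning carries over to Days 4–13 and a different site is used, the previous site has no 72 h rating at all. Section 5.2 names the upper arm (or the abdomen) but gives no rule on site rotation or identification, so it does not settle this.

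**Effect of adding Days 2, 5, 9 and 12:** these days fall 24, 24, 48 and 48 h after doses 1–4.

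- Doses 1 and 2: checks at 4, 24 and 72 h; gaps of 20 and 48 h.
- Doses 3 and 4: checks at 4, 48 and 72 h; gaps of 44 and 24 h.

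The longest gap within a dosing interval falls from 68 h to 48 h.

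**The case against.** The strongest reply is that Part B is not blind between checks. Subjects are in-house throughout dosing, observed for signs and symptoms and questioned at least daily (Section 7.3.1). AE recording is continuous, a physician reviews each subject's data before every dose (Section 3.1.2), and extra assessments are allowed at discretion (Section 7.3). This stands. A reader might infer from the schedule that reactions in the 68 h window would go unobserved; the documents do not support that. What is missing is a scheduled grade, which matters mainly for mild or moderate signs that nobody reports.

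A reader might also infer that worsening with repeated injection cannot be judged. That does not follow either. The 4 h check is made after all five doses in the same subjects, which gives a like-time, within-subject comparison. Only the time-matched comparison with Part A is limited, and that comparison is not a stated objective (Section 2.1).

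A third tempting step is to say that the toxicology predicts the reactions this schedule would miss. Section 1.4 does report that "microscopic findings included mononuclear cell infiltrates at the SC injection sites of animals" given repeated doses, and similar findings in rats. But these were microscopic, were judged non-adverse, persisted through recovery in rats at the top dose and had not resolved by the end of recovery in monkeys. They arose at 10 nmol/kg and above, about 46.2 µg/kg, against 0.333 µg/kg for the highest planned single dose in Table 1, a ratio of roughly 139. They do not point to reactions that come and go within three days.

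Finally, Part B has more scheduled checks per subject overall after the first dose: 5 + 4 + 4 = 13 over 57 days, against 6 + 3 = 9 over 28 days in Part A. That is true, but the total does not fill the window after each of doses 1–4.

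**Conclusion.** The point holds as a modest weakness in how a primary safety endpoint is sampled. It is not an error or a contradiction in the plan. After Part B doses 1–4 there is no scheduled graded check for 68 of each 72 h, and Grade 1–2 reactions confined to that window depend on being noticed or volunteered. Graded incidence may therefore be understated; the documents give no reaction rate or time course, so only the direction can be stated.

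This rests on two assumptions. The first is that dosing stays at 72 h intervals, although Section 3.1.2 allows the frequency to change after Part A. The second is that the predose check on Days 4–13 covers the previous injection site; if it does not, coverage of earlier sites is thinner than stated here.

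**What to change.** In the Part B study plan, add the Section 7.3.8 assessment on Days 2, 5, 9 and 12. In Section 7.3.8, state that the predose checks on Days 4, 7, 10 and 13 re-inspect the previous injection site, and have each site identified so that this can be done. Matching the full set of Part A times after the first and last doses would improve comparability between the parts, but is optional.

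The cost is a few minutes of inspection at contacts that already take place, with no new visits or staff. It adds four assessments per subject: 4 × 24 = 96 more CRF entries for the planned Part B subjects, or 4 × 48 = 192 if all three additional groups are used. Appendix 7 records that a Part A laboratory timepoint was added by a non-substantial amendment, so there is a precedent for a schedule change of this kind.

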Appendix 7: Protocol Amendment Summary of Changes

Protocol Amendment 3 (Version 2.2; 12 December 2018)

This non-substantial amendment has been issued to include a clinical laboratory assessment on Day -2 in Part A.

Appendix 3

Additional clinical laboratory sample added to Part A. Total blood volume withdrawn in Part A updated to 124.5 mL.

Appendix 6 Study Plan (Part A)

Clinical chemistry, haematology, and urinalysis assessment added on Day -2.

Protocol Amendment 2 (Version 2.1; 29 November 2018)

This non-substantial amendment has been issued to correct minor inconsistencies in PK sampling timepoints, data cut off for dose escalation, clinical laboratory assessment timepoints, and the synopsis. Additionally, details of the injection site assessments have been added to the protocol.

A detailed summary of changes is presented below. For each section, deleted text is shown in ~~strike through~~, and new text is shown in **bold**:

Synopsis: Endpoints

Text added:

Safety:

Adverse events, clinical laboratory evaluations (clinical chemistry, hematology, urinalysis), 12-lead ECGs, vital signs measurements, injection site assessment, **heat pain threshold and tolerance**, and physical examinations.

Section 3.6

Previously read:

In Part A, doses will be administered in an escalating manner following satisfactory review by the Sponsor and Investigator of the safety, and tolerability data up to Day-7 (144 hours postdose) from groups that received lower doses of OLP-1002.

Now reads:

In Part A, doses will be administered in an escalating manner following satisfactory review by the Sponsor and Investigator of the safety, and tolerability data up to

Day **10** (216 hours postdose) from groups that received lower doses of OLP-1002.

Section 7.3.8

Entire section added to describe injection site assessments.

Appendix 3

Total blood volume for PK analysis (76 mL) added.

Appendix 6 - Schedule of assessments Part A

24 hour postdose continuous ECG recording timepoint added.

Appendix 6 - Schedule of assessments Part B

Clinical chemistry, haematology, and urinalysis for Days 1-15 previously read:

Days 2, 4, 7, ~~10,13~~

Clinical chemistry, haematology, and urinalysis for Days 1-15 now reads:

Days 2, 5, 9, 12, 17

PK blood sampling for Days 1-15 previously read:

Day 1 and Day ~~15~~: Pre dose, 0.5, 1, 1.5, 2, 3, 4, 6, 8 and 12 hours post dose
Days 4, 8, ~~11, 15~~ Predose

PK blood sampling for Days 1-15 now reads:

Day 1 and Day **13**: Pre dose, 0.5, 1, 1.5, 2, 3, 4, 6, 8 and 12 hours post dose
Days 4, 7, **10** Predose

Day 15

Protocol Amendment 1 (Version 2; 02 October 2018)

This amendment has been generated following the non-acceptance of the original protocol (version 1) by the Medicines and Healthcare products Regulatory Agency (MHRA) on 20 September 2018. All changes made have been in response to comments provided by the MHRA.

The primary changes in this amendment are:

1. Inclusion of PK sampling in Parts A and B:
 - PK objective and exploratory endpoints added (Section 2).

- Discussion of PK included Section 3.4.
 - PK stopping criteria added to Section 3.7.
 - PK assessments included in Section 7.1.
 - PK population and analysis (Section 8.2.1).
 - Blood volumes updated to include samples for PK assessments (Appendix 3).
2. Exclusion and stopping criteria updated
 - Women who are pregnant or breastfeeding have been excluded from the study (Section 4.2).
 - Liver function tests, tachycardia, and hypertension stopping criteria have been updated (Section 3.7 and Section 4.4).
 - Stopping criteria for SAEs and serious AEs have been added (Section 3.7 and Section 4.4).
 3. Safety, tolerability, and PK data up to Day 22 in Part B will be reviewed prior to dose escalation (Section 3.1.2).
 4. Sentinel dosing included in Part B (Section 3.1.2).
 5. It has been specified that the maximum dose for additional groups will not exceed 20 µg (Section 3.5.3).

Minor changes:

1. Additional clinical laboratory evaluations have been included on Day 14 in Part A.
2. The definition of the Safety population has been updated to include all subjects who receive OLP-1002.
3. Typographical errors and formatting errors were corrected, as necessary.

A detailed summary of changes is presented below. For each section, deleted text is shown in ~~strike through~~, and new text is shown in **bold**:

Section 1.6

Previously read:

This information, together with the pharmacodynamic (PD) data, will help establish the doses and dosing regimen suitable for future studies in patients.

Now reads:

This information, together with the pharmacodynamic (PD) **and pharmacokinetic (PK)** data, will help establish the doses and dosing regimen suitable for future studies in patients.

Section 2.1

Objective added:

Where possible, single and/or multiple subcutaneous dose pharmacokinetics of OLP-1002 in healthy subjects will be determined.

Section 2.2.1

Endpoint added:

- **demonstrate that exposure to OLP-1002 does not exceed pre-defined exposure limits from non-clinical studies.**
-

Section 2.2.2

Endpoints added:

- **For Part A, the single ascending dose, PK outcome endpoints of OLP-1002 are as follows:**

Primary PK

- **area under the plasma concentration-time curve (AUC) from time zero to infinity (AUC_{0-∞}) (actual and dose normalized [DN])**
- **AUC from time zero to the time of the last quantifiable concentration (AUC_{0-tlast}) (actual and DN)**
- **maximum observed plasma concentration (C_{max}) (actual and DN)**

Secondary PK

- **time of the maximum observed plasma concentration (t_{max})**
- **apparent plasma terminal elimination half-life (t_{1/2})**
- **For Part B, the multiple ascending dose PK outcome endpoints of OLP-1002 are as follows:**

Primary PK

- **AUC over a dosing interval (AUC_{0-τ}) (actual and DN)**
- **AUC_{0-∞} (actual and DN)**
- **C_{max} (actual and DN)**

Secondary PK

- **minimum observed plasma concentration (C_{min})**
 - **t_{max}**
 - **t_{1/2}**
 - **observed accumulation ratio based on AUC_{0-τ} (RAAUC_{0-τ})**
-

- **observed accumulation ratio based on C_{max} (RAC_{max}).**
- **Temporal change parameter (TCP)**

Other PK parameters may also be added if deemed necessary.

Section 3.1.1

Previously read:

Part A will comprise a single-dose, sequential-group design. Overall, 44 healthy subjects will be studied in 8 groups. Up to 3 additional groups (24 subjects in total) may be included for further assessment of safety, tolerability, and PD (Section 3.3).

Potential subjects will be screened to assess their eligibility to enter the study within 28 days prior to the first dose administration. Potential subjects for Groups A2, A4, and A6 will attend a pre-screening visit for an intradermal capsaicin test (Section 3.4.2).

Each subject will participate in 1 treatment period only, and will reside at the Clinical Research Unit (CRU) from Day -2 (2 days before dosing) to Day 3. All subjects will return for non-residential visits on Days 4, 7 (± 2 days), 10 (± 2 days), and 14 (± 2 days), and for a poststudy visit on Day 28 (± 2 days).

Based on the ongoing review of the safety and tolerability, additional non-residential visits may be required. The number of additional visits per subject will not exceed 3 and will not extend beyond Day 28 (± 2 days).

Doses will be administered in an escalating manner following satisfactory review of safety and tolerability data up to Day 7 (144 hours postdose) from the lower dose levels.

Now reads:

Part A will comprise a single-dose, sequential-group design. Overall, 44 healthy subjects will be studied in 8 groups. Up to 3 additional groups (24 subjects in total) may be included for further assessment of safety, tolerability, **PK**, and PD (Section 3.3).

Potential subjects will be screened to assess their eligibility to enter the study within 28 days prior to the first dose administration. Potential subjects for Groups A2, A4, and A6 will attend a pre-screening visit for an intradermal capsaicin test (Section 3.4.2).

Each subject will participate in 1 treatment period only, and will reside at the Clinical Research Unit (CRU) from Day -2 (2 days before dosing) to Day 3. All subjects will return for non-residential visits on Days 4, 7 (± 2 days), 10 (± 2 days), and 14 (± 2 days), and for a poststudy visit on Day 28 (± 2 days).

Based on the ongoing review of the safety and tolerability, additional non-residential visits may be required. The number of additional visits per subject will not exceed 3 and will not extend beyond Day 28 (± 2 days).

Doses will be administered in an escalating manner following satisfactory review of safety and tolerability data up to Day 10 (216 hours postdose) from the lower dose levels. **For doses $\geq 12 \mu\text{g}$, PK data will also be reviewed up to Day 7 prior to dose escalation.**

Figure 1 – footnote

Text added:

Groups A9 to A11 may be included if required; **dose levels will not exceed the maximum proposed dose of 20 μg .**

Figure 2 – footnote

Text added:

Groups B4 to B6 will be included if required; **dose levels will not exceed the maximum proposed dose of 20 μg .**

Section 3.1.2

Previously read:

In each of Groups B1 to B3, 6 subjects will receive OLP-1002 and 2 subjects will receive placebo. ~~There will be no sentinel dosing in Part B.~~ For all subjects, a single subcutaneous dose will be administered on Days 1, 4, 7, 10, and 13. The dosing frequency in Part B may be changed following review of data from groups in Part A (Section 3.4).

Doses will be administered in an escalating manner following satisfactory review of safety ~~and~~ tolerability data up to Day 18 (~~120~~ hours post-final dose) from the lower dose levels. Part B may start after a review of the safety ~~and~~ tolerability for Groups A1 to A6. The total daily dose administered will not exceed the highest single dose given in Part A.

Now reads:

In each of Groups B1 to B3, 6 subjects will receive OLP-1002 and 2 subjects will receive placebo. For all subjects, a single subcutaneous dose will be administered on Days 1, 4, 7, 10, and 13. Prior to each dosing occasion a physician will review the available safety and tolerability data from each subject to confirm it is acceptable to continue dosing. The dosing frequency in Part B may be changed

following review of data from groups in Part A (Section 3.4).

Sentinel dosing will only occur in Part B at dose levels where exposure to OLP-1002 at steady state is predicted to exceed exposures that have been shown to be safe and well tolerated in earlier groups in Parts A or B. In the event of sentinel dosing, 2 subjects (1 active, 1 placebo) will be dosed at least 4 days prior to the remaining 6 subjects (5 active: 1 placebo). Safety data for the sentinel subjects from at least 2 additional doses will be reviewed prior to dosing the remaining subjects (i.e. sentinel subjects' safety data after doses 1 and 2 will be reviewed prior to the remaining subjects receiving dose 1). In addition, safety data from each subject will be reviewed by a physician prior to each dose to approve continued dosing.

Doses will be administered in an escalating manner following satisfactory review of safety, tolerability, **and PK** data up to Day **22 (216 hours post-final dose)** from the lower dose levels. Part B may start after a review of the safety, tolerability, **and available PK data** for Groups A1 to A6. The total daily dose administered will not exceed the highest single dose given in Part A.

Section 3.3

Previously read:

Following review of the safety, tolerability, and PD data, additional dose groups may be added to the study.

Now reads:

Following review of the safety, tolerability, **PK**, and PD data (**where systemic exposure is not expected to exceed that stated in the dose escalation stopping criteria [Section 3.7]**), additional dose groups may be added to the study. **The maximum dose for any additional group will not exceed 20 µg.**

Section 3.4

Previously read:

Healthy male and female subjects will be recruited into this study. The inclusion of females of childbearing potential is in accordance with International Council for Harmonisation (ICH) M3, based on the short dosing duration (< 2 weeks).

In Part A, it is anticipated that groups of 4 subjects (3 active: 1 placebo) will be sufficient in order to determine safety and tolerability. In order to assess the PD effects of OLP-1002, 3 groups in Part A will include 8 subjects (6 active; 2 placebo). A full review of the safety and tolerability data from Part A will be performed to determine the dose regimen for Part B. Part B may start after a full review of all safety and tolerability data from Group A1 to A6. A review of PD data

may also be performed, at the discretion of the Investigator. Details of the dosing regimen and duration used for Part B of the study will be documented in the TMF.

Based upon the nonclinical data, the duration of a 28-day follow-up in Part A, and a 57-day follow-up in Part B is considered adequate to achieve the study objectives.

Based upon the nonclinical data, the duration of a 28-day follow-up in Part A, and a 57-day follow-up in Part B is considered adequate to achieve the study objectives.

~~Pharmacokinetic analysis will not be conducted in this study.~~ The bioanalytical method used for preclinical species has a lower limit of quantification (LLOQ) of 5 ng/mL. The increased sample volume possible from humans (compared to small animals) may afford an approximate 10-fold increase in sensitivity with possibly an additional 5-fold increase from the use of a more sensitive mass spectrometer. This could potentially deliver an LLOQ of around 0.1 ng/mL. It is apparent from the predicted plasma concentrations (see Section 3.5.2) that only a small number of samples around C_{max} at the highest doses would be quantifiable and that a conventional approach to pharmacokinetic will not achieve a full definition of the plasma concentration vs time profile or enable an estimation of the terminal phase. ~~Thus, the additional burden of sampling procedures would not be justified by the quality of the data which it would generate.~~

Now reads:

In Part A, safety data up to Day 10 will be reviewed prior to dose escalation, and PK data up to Day 7 will be reviewed for all groups receiving $\geq 12 \mu\text{g}$ OLP-1002. In Part B, safety, tolerability and PK data up to Day 22 will be reviewed for all dose groups. As the $t_{1/2}$ of OLP-1002 is predicted to be approximately 180 hours (based on non-clinical data) review of safety data up to Day 10 (Part A) and Day 22 (Part B) is considered sufficient to ensure data from at least one half-life is included in the review. In addition, as plasma exposures are anticipated to be low, it is expected that it will only be possible to perform an assessment of peak concentrations (C_{max}) and therefore PK data to Day 7 (Part A) and Day 22 (Part B) will be sufficient. Additionally, a cumulative safety review will occur such that additional emerging safety data from earlier groups will be considered when making a dose escalation decision.

Healthy male and female subjects will be recruited into this study. The inclusion of females of childbearing potential is in accordance with International Council for Harmonisation (ICH) M3, based on the short dosing duration (< 2 weeks).

In Part A, it is anticipated that groups of 4 subjects (3 active: 1 placebo) will be sufficient in order to determine safety and tolerability. In order to assess the PD effects of OLP-1002, 3 groups in Part A will include 8 subjects (6 active; 2 placebo). A full review of the safety and tolerability data from Part A will be performed to determine the dose regimen for Part B. Part B may start after a full review of all safety and tolerability data from Group A1 to A6. A review of PD data may also be performed, at the discretion of the Investigator. Details of the dosing

regimen and duration used for Part B of the study will be documented in the TMF.

Based upon the nonclinical data, the duration of a 28-day follow-up in Part A, and a 57-day follow-up in Part B is considered adequate to achieve the study objectives.

Pharmacokinetic analysis in Part A will initially only be conducted for groups receiving $\geq 12 \mu\text{g}$ OLP-1002, with retrospective analyses of samples from lower dose groups occurring in the event of PK data being quantifiable at doses $\geq 12 \mu\text{g}$ and if supported by bioanalytical stability data. Dose escalation decisions for doses $<12 \mu\text{g}$ in Part A will not require PK data. The rationale for this is that maximum plasma concentrations at $12 \mu\text{g}$ are expected to be approximately 0.078 ng/mL and the bioanalytical method used for preclinical species has a lower limit of quantification (LLOQ) of 5 ng/mL . The increased sample volume possible from humans (compared to small animals) may afford an approximate 10-fold increase in sensitivity with possibly an additional 5-fold increase from the use of a more sensitive mass spectrometer. This could potentially deliver an LLOQ of around 0.1 ng/mL . Therefore, even with the increased assay sensitivity plasma levels from doses at or below $12 \mu\text{g}$ are not expected to be quantifiable. It is apparent from the predicted plasma concentrations (see Section 3.5.2) that only a small number of samples around C_{max} at the highest dose would be quantifiable and that a conventional approach to pharmacokinetic will not achieve a full definition of the plasma concentration vs time profile or enable an estimation of the terminal phase. **In addition the planned dose levels have a high safety margin when comparing the predicted exposures to the exposures at the NOAEL (see Section 3.5.2), with the $12 \mu\text{g}$ dose level having an expected 312-fold and 255-fold safety margin based on C_{max} and $\text{AUC}_{0-\infty}$, respectively. Therefore if exposure is significantly higher than predicted it is not expected to exceed the PK stopping criteria.**

Section 3.4.1

Previously read:

~~In Part B, all subjects in a group will be dosed on the same day.~~ Accumulation of OLP-1002 is expected following multiple doses, based on the preclinical data, and will be taken into account when determining the doses for Part B (see Section 3.5.3).

Now reads:

In Part B, sentinel dosing will be used in groups where exposure to OLP-1002 at steady state is predicted to exceed exposures that have been shown to be safe and well tolerated in earlier groups in Parts A or B. When used, two subjects (1 active; 1 placebo), will be dosed 4 days prior to the remaining 6 subjects (5 active; 2 placebo). The 2 sentinel subjects will always be 2 doses ahead of the remaining subjects (ie. sentinel subjects will receive dose 2 before the

remaining subjects receive dose 1). Subjects in groups where exposure is not predicted to exceed that tested in Part A will be dosed on the same day.

Accumulation of OLP-1002 is expected following multiple doses, based on the preclinical data, and will be taken into account when determining the doses for Part B (see Section 3.5.3). **If it is not possible to quantify exposure it will be assumed that multiple dosing results in a 4-fold accumulation based on the predicted $t_{1/2}$ of 180h.**

Section 3.5.3

Text added:

If additional groups (A9-11 or B3-6) are required, the maximum daily dose administered will not exceed 20 µg and predicted systemic exposure will not exceed that stated in the dose escalation stopping criteria [Section 3.7]) based on available PK data.

Section 3.6

Previously read:

In Part A, doses will be administered in an escalating manner following satisfactory review by the Sponsor and Investigator of the safety, and tolerability data up to Day 7 (144 hours postdose) from groups that received lower doses of OLP-1002.

In Part B, doses will be administered in an escalating manner following satisfactory review of safety ~~and~~ tolerability data up to Day ~~18~~ (120 hours post-final dose) from groups that received lower doses of OLP-1002. Doses may be reduced and may be lower than the starting dose.

Dose escalation in Part A will only occur if data from a minimum of 4 subjects (Groups A1, A3, A5, A7, and A8) or 6 subjects (Groups A2, A4, and A6) have been reviewed from the previous lower dose group, such that data from a minimum of 5 subjects, who have received OLP-1002 will be used to make the dose-escalation decision. Dose escalation in Part B will only occur if data from a minimum of 6 subjects have been reviewed from the previous lower dose group, such that data from a minimum of 4 subjects who have received OLP-1002 will be used to make the dose-escalation decision.

Now reads:

